12.2.1.3 Subgroup analysis

Subgroup analyses will be conducted to assess consistency of treatment effect across potential or expected prognostic factors, including the baseline stratification factors.

If there are too few results available for a meaningful analysis of a particular subgroup (it is not considered appropriate to present analyses where there are less than 5 events in either treatment group), the relationship between that subgroup and IDFS will not be formally analysed. In this case, only descriptive summaries will be provided.

The following subgroups are of primary interest:

- Hormone receptor status (ER and/or PgR positive and HER2 negative; TNBC)
- Neoadjuvant chemotherapy; adjuvant chemotherapy
- Prior platinum therapy for current breast cancer (Yes; No)
- BRCA mutation type (BRCA1; BRCA2; BRCA1/2 both)
- Hormone receptor status by prior chemotherapy setting (if there are sufficient events to split into the four groups)
 - ER and/or PgR positive with neoadjuvant chemotherapy
 - ER and/or PgR positive with adjuvant chemotherapy
 - ER and PgR negative with neoadjuvant chemotherapy
 - ER and PgR negative with adjuvant chemotherapy
- *BRCA* status by prior platinum therapy setting
 - *BRCA1* with prior platinum therapy for current breast cancer

- BRCA1 with no prior platinum therapy for current breast cancer
- BRCA2 with prior platinum therapy for current breast cancer
- BRCA2 with no prior platinum therapy for current breast cancer

The following additional subgroups will also be analysed to assess consistency in treatment effect across a broader set of baseline characteristics known before start of study medication:

- Type of prior Neo/Adjuvant chemotherapy (anthracycline; taxane; anthracycline plus taxane)
- Type of breast surgery prior to randomisation (breast conservation; unilateral mastectomy; bilateral mastectomy)
- Bilateral Oophorectomy (Yes; No)
- Axillary nodal status at surgery prior to randomisation (Positive or negative for the post adjuvant patients only)
- CPS+EG score baseline (2, 3 or 4; 5 or 6 for the post neoadjuvant group only)
- Age at randomisation (< 50; 50-64; ≥ 65)
- Race
- Sponsor (AZ; NRG Oncology)

Other baseline variables may also be assessed if there is clinical justification. These would be pre-defined within the SAP.

For each subgroup, the HRs (olaparib: placebo) and associated CIs will be calculated from a Cox proportional hazards model (using the Efron approach for handling ties) that contains the treatment term, factor and treatment-by-factor interaction term. The treatment effect HRs for each treatment comparison along with their confidence intervals will be obtained for each level of the subgroup from this single model. The HRs and 95% CIs will be presented on a forest plot including the HR and 95% CI from the overall population (using the primary analysis).

No adjustment to the significance level for testing subgroups will be made since all these subgroup analyses will be considered exploratory. The results would be used as supportive data for the primary analysis of IDFS based on all randomised patients.

12.2.1.4 Analysis of interaction

The presence of quantitative interactions will be assessed by means of an overall global interaction test. This will be performed in the overall population by comparing the fit of a Cox proportional hazards model including treatment, all covariates (including stratification factors), and all covariate-by-treatment interaction terms, with one that excludes the interaction terms and will be assessed at the 2-sided 10% significance level. If a covariate does not have more than 20

events per level (of the covariate) it will be included as a covariate in the model, but the covariate-by-treatment interaction term will be omitted. If the fit of the model is not significantly improved then it will be concluded that overall the treatment effect is consistent across the subgroups.

If the global interaction test is found to be statistically significant, an attempt to determine the cause and type of interaction will be made. Stepwise backwards selection will be performed on the saturated model, whereby (using a 10% level throughout) the least significant interaction terms are removed one-by-one and any newly significant interactions re-included until a final model is reached where all included interactions are significant and all excluded interactions are non-significant. Throughout this process all main effects will be included in the model regardless of whether the corresponding interaction term is still present. This approach will identify the factors that independently alter the treatment effect and prevent identification of multiple correlated interactions.

Any quantitative interactions identified using this procedure will then be tested to rule out any qualitative interaction using the approach of [Gail and Simon 1985](#).

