This is a collaborative study being coordinated worldwide by the Breast International Group (BIG) in partnership with Frontier Science (FS), NRG Oncology (NCI supported National Clinical Trials Network Group) and AstraZeneca (AZ). Two versions of this protocol have been written to cover this global adjuvant breast cancer study. One protocol version covers all patients recruited outside of the US (where AZ is the sponsor) and one protocol version covers patients recruited within the US (where NRG Oncology is the sponsor). The two versions of the protocol are identical in terms of study objectives and scientific content and only differ in logistical content appropriate for the country(ies) they cover (i.e. drug distribution, mechanisms for SAE reporting during the study, etc.). Based on current recruitment rates, it is expected that approximately 230 patients will be randomised under the US protocol and approximately 1570 patients will be randomised under the Rest of the World protocol.

The trial will use one randomisation system and report as one single study. The initial collection of the patients' data will be done using two databases (one for the US patients and one for all other patients outside of the US). The two databases will be set up using the same standards and eCRFs to ensure consistency in the data collection. The data from both databases will be combined into a single consolidated database at regular, pre-specified intervals. All study endpoints as well as reports for periodic review by the Independent Data Monitoring Committee

(IDMC) will be analysed and reported from the single combined reporting database held by Frontier Science on behalf of BIG.

Study design

This is a randomised, double-blind, parallel group, placebo-controlled multi-centre Phase III study to assess the efficacy and safety of olaparib versus placebo as adjuvant treatment in patients with germline *BRCA1/2* mutations and high risk HER2 negative primary breast cancer who have completed definitive local treatment and neoadjuvant or adjuvant chemotherapy.

Patients will be randomised in a 1:1 ratio to either olaparib or placebo. Randomisation will be stratified by hormone receptor status (ER and/or PgR positive/HER2 negative versus TNBC), by prior neoadjuvant versus adjuvant chemotherapy, and prior platinum use for breast cancer (yes versus no).

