2.4 Exploratory objectives

The exploratory objectives of this study are:

1. To assess the consistency of treatment effects on efficacy endpoints across potential or expected prognostic factors, including the baseline stratification factors with special emphasis on hormone receptor status.
2. To explore methods for estimating overall survival (OS) adjusting for the impact of confounding by subsequent therapies, specifically the control arm receiving subsequent Polyadenosine 5'diphosphoribose [poly (ADP ribose)] polymerisation (PARP) inhibitors or platinum salts
3. To explore whether resistance mechanisms to olaparib can be identified through analysis of tumour and blood sample derivatives (cells, plasma and protein and nucleic acid derivatives) - archival tumour samples (mandatory*), tumour sample at recurrence (optional), and blood samples at baseline, 30 days post study treatment and on disease recurrence (mandatory)

*For adjuvant patients, this refers to the surgical specimen; for neoadjuvant patients, both the pre-treatment core biopsy and the surgical specimen with residual disease are requested, but only one is mandatory. If the surgery tumour blocks are available, but cannot be submitted, sites may submit a portion of invasive tumour from the original block, either by taking at least one core of at least 3 mm in diameter, or by splitting the original block in two parts, and re-embedding one in a new block for central submission. If blocks containing pre-neoadjuvant treatment core biopsies are available but cannot be submitted, sections mounted on glass slides prepared from the block can be provided. If tumour sample can't be provided as requested above or if it's not available, approval by Study Team for patient's entry into the trial is required.

4. To determine the frequency of and describe the nature of *BRCA* mutation/s in tumour samples and to compare this with germline *BRCA* mutation status
5. To conduct future exploratory research into factors that may influence development of cancer and/or response to treatment (where response is defined broadly to include efficacy, tolerability or safety). This may be performed on the collected and stored tumour and blood samples

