We assume that half of triple negative patients and a quarter of hormone receptor positive patients will have received neoadjuvant chemotherapy and we anticipate that 95% of patients enrolled in the trial will complete the HRQoL instrument. In addition, adjusting downward to allow for 20% of missing data at the 12 months assessment point, we expect that data from 633 neoadjuvant and 735 adjuvant patients will be available (assuming that 15% of the total 1800 enrolled patients are ER and/or PgR positive HER2 negative). These will be sufficient to provide statistical power of 93% and 96% correspondingly to detect a difference of 3 points on the FACIT-Fatigue scale score between treatment groups assuming a standard deviation of 10.9 ([Cella D et al 2002](#)) (estimated SD of mean baseline score) and controlling α -level at 0.05. The 3-point difference is the clinically meaningful difference reported by the developers of the scale ([Cella D et al 2002](#)), and we are hypothesizing that the olaparib arm will be worse. A collection of PROs and QOL from all patients enrolled in the main trial will give us sufficient statistical power to detect important differences between two treatment groups.

Missing PRO data

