12.2.7 Sample size justification

The primary endpoint of the study is IDFS and patients will be randomised 1:1 to either olaparib 300 mg b.i.d. (twice daily) or matching placebo.

A total of 1800 patients will be randomised into the study to achieve 330 IDFS events. If the true HR for the comparison of olaparib versus placebo in terms of IDFS is 0.7 then with 330 events, the analysis of IDFS will have 90% power to demonstrate a statistically significant difference in IDFS, assuming a 2-sided 5% significance level. The critical HR value at the primary analysis is 0.805.

The actual accrual pattern between June 2014 and February 2018 is shown in [Table 16](#).

It is estimated that 1800 patients will be randomised by April/May 2019 so that the study will take approximately 5 years to complete recruitment (approximately 230 patients in US and approximately 1570 patients in the Rest of the World countries).

Table 16 Actual accrual between June 2014 and February 2018

Interval since start of randomisation (months)	Number of patients randomized in interval	Cumulative number of patients randomized	Average number of patients randomized per month in interval
0-6	21	21	3.5
6-12	94	115	15.7
12-18	174	289	29
18-24	180	469	33
24-30	229	698	38.2
30-36	249	947	41.5
36-42	234	1181	39
42-45*	118	1299	39.3

*Note: 3-month interval: December 2017 to February 2018 inclusive.

The primary analysis population will be all patients randomised (ITT). A subgroup analysis based on prior chemotherapy (adjuvant or neoadjuvant), prior platinum therapy (yes or no) and hormone receptor status (ER and/or PgR positive/HER2 negative versus TNBC) will be conducted to check for consistency in the treatment effect but this analysis is considered supportive of the primary analysis in the overall population.

During the trial, the Steering Committee will monitor the recruited patient population and actual event rate whilst remaining blinded to treatment. If the data suggests that the original sample size assumptions are incorrect such that achieving the required number of events with the current number of patients does not seem feasible then in consultation with the IDMC a decision may be made to increase the number of patients recruited into the trial to achieve the required 330 events.

12.2.8 Issues relating to racial and ethnic differences in the U.S.

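### Section 12.2.1.4 reads a non-significant pooled interaction test as proof of a consistent treatment effect, which a test that misses a null effect in hormone-receptor-positive patients about 77-85% of the time cannot supply

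*Protocol*

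**What the plan says.** Section 12.2.1.4 compares two Cox models. Both contain treatment and all covariates, including the stratification factors, and one adds every covariate-by-treatment interaction. The comparison is made at a two-sided 10% level. An interaction term is omitted if its covariate does not have more than 20 events per level. The section then states: "If the fit of the model is not significantly improved then it will be concluded that overall the treatment effect is consistent" across the subgroups. Only after a significant result does it go on to backward selection of individual interactions. Any quantitative interaction found that way "will then be tested to rule out any qualitative interaction" by the Gail-Simon method.

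Section 2.4 makes consistency of effect the first exploratory objective, across prognostic factors "including the baseline stratification factors with special emphasis on hormone receptor status".

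Section 12.2.1.3 separately fits, for each subgroup factor, a Cox model with treatment, factor and their interaction. It shows the hazard ratio (HR) and 95% confidence interval for each level on a forest plot. It calls all subgroup analyses exploratory and supportive of the primary result.

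**The concern.** The rule turns absence of evidence into a positive finding. A likelihood-ratio test that fails to reject says only that the data do not show heterogeneity at the chosen level. Whether that is informative depends on power, and section 12.2.1.4 gives neither power nor a margin. A pooled test spreads its power over many directions, so a difference confined to one factor is diluted. Hormone receptor status, the factor singled out in section 2.4, is one degree of freedom among them, and on the protocol's own assumption its smaller level is small.

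The Gail-Simon sentence makes the same mistake. The null hypothesis of that test is that no qualitative interaction exists, so a non-significant result does not rule one out.

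At stake is how the report describes the result for hormone-receptor-positive patients. Section 1.3 supports the expected benefit in them partly by extrapolation from the metastatic setting. If olaparib had no effect in this group, the rule as written would still usually lead to a statement that the effect is consistent.

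**Working it through.** **Inputs from the protocol.** Section 12.2.7: "If the true HR for the comparison of olaparib versus placebo in terms of IDFS is 0.7 then with 330 events", "90% power to demonstrate a statistically significant difference in IDFS, assuming a 2-sided 5% significance level". Synopsis: "Patients will be randomised in a 1:1 ratio to either olaparib or placebo". Section 12.2.1.4: interaction test at 10%. Section 12.2.3.2: "assuming that 15% of the total 1800 enrolled patients are ER and/or PgR positive HER2 negative".

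**Assumed, because the protocol does not fix them.**
- The hormone-receptor-positive share of events equals the 15% share of patients (other shares are tried below).
- The pooled test has 6 to 16 interaction degrees of freedom (df). Section 12.2.1.4 does not list the covariates; the range is judged from the factors in section 12.2.1.3 and the 20-event rule.
- No other factor interacts with treatment.

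**Reproducing the plan's figures.** Schoenfeld's formula gives 4(1.960 + 1.282)² / (ln 0.7)² = 331 events, and power with 330 events is 0.8997, against the stated 90%. The critical HR is exp(−1.96 × 2/√330) = 0.806; the protocol says "The critical HR value at the primary analysis is 0.805". The 15% share also reproduces the 633 and 735 patients in section 12.2.3.2: (0.5 × 1530 + 0.25 × 270) × 0.95 × 0.8 = 632.7 and (0.5 × 1530 + 0.75 × 270) × 0.95 × 0.8 = 735.3.

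**Power of the pooled test.** Events split 0.15 × 330 = 49.5 against 280.5. The standard error of the log ratio of HRs is √(4/49.5 + 4/280.5) = 0.308. The noncentrality is (difference in log HR / 0.308)², and power is the probability that a noncentral chi-square exceeds the central 90% point.

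Two TNBC effects are used with HR 1.0 in hormone-receptor-positive patients. HR 0.70 puts the design value in TNBC. HR 0.65 is close to exp(ln 0.7/0.85) = 0.657, the value that keeps the overall HR at 0.7. The noncentralities are 1.34 and 1.95.

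| Interaction df | Missed, 0.65 v 1.0 | Missed, 0.70 v 1.0 |
|---|---|---|
| 6 | 77% | 81% |
| 8 | 79% | 82% |
| 12 | 81% | 84% |
| 16 | 82% | 85% |
| 1 (hormone receptor status alone) | 60% | 69% |

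Power of the pooled test is thus about 15-23%, against a 10% false-positive rate. A simulated 12-df Cox likelihood-ratio test (1800 patients, 330 events, 600 replicates) with 0.70 v 1.0 rejected in 16.7%, so it missed 83%. With a uniform effect it rejected in 11%.

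**Other event shares, 6 to 16 df, HR 1.0 in hormone-receptor-positive patients.**

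| Share of events | Missed, TNBC HR 0.70 | Missed, overall HR held at 0.7 |
|---|---|---|
| 10% | 84-86% | 82-86% |
| 15% | 81-85% | 77-83% |
| 25% | 76-82% | 65-75% |
| 30% | 75-81% | 57-70% |

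**Gail-Simon.** Take true HRs of 0.65 and 1.3 with 280.5 and 49.5 events. Rejection needs both level-specific z values beyond 1.645 (5% level) or 1.282 (10% level) in opposite directions. Power is 0.230 or 0.357, so the test misses 77% or 64%. The plan applies it only to interactions already selected as significant, which softens this. The 1-df interaction test at 10% has power 0.727 here, and a Gail-Simon rejection at either level implies that test is significant. Given a significant interaction, the miss rate is 1 − 0.230/0.727 = 68% or 1 − 0.357/0.727 = 51%.

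**The case against.** Much of the case on the other side stands.

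- **Hormone receptor status is examined.** A reader might infer that, because the procedure in 12.2.1.4 stops after a non-significant global test, the hormone-receptor interaction would never be looked at. The protocol does not support that. Section 12.2.1.3 lists hormone receptor status first among the subgroups of primary interest, fits the treatment-by-factor model unconditionally and reports both HRs with 95% intervals. With 49.5 events and a true HR of 1.0, the expected interval is exp(±1.96 × 2/√49.5), about 0.57 to 1.75, so the lack of information would be visible. Section 12.2.7 also plans a hormone-receptor subgroup analysis as a consistency check.
- **No decision depends on it.** The primary test, the multiple testing procedure and the interim and futility rules do not use the interaction test, and the subgroup analyses are labelled exploratory.
- **Most of the low power comes from trial size.** The 1-df test also misses 60-69%; pooling adds roughly 12 to 22 points. A global screen is a recognised guard against false positives across many factors. A reader might infer that a 1-df hormone-receptor test should take the lead, but that is a preference, and its own power is poor.
- **The size rests on assumptions.** The 15% is a patient share from the patient-reported-outcome sample size, and section 1.3 says event rates may differ between phenotypes. The degrees of freedom and the TNBC HR are also chosen here.

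None of this rescues the sentence itself. Low power under any test is a reason not to conclude consistency from non-rejection. The exploratory label limits the consequence but does not make the inference valid.

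**Conclusion.** The rule is wrong as written. The protocol commits to declaring the effect consistent on the basis of a test that, at 330 events, would miss a complete absence of effect in hormone-receptor-positive patients about 77-85% of the time. That figure assumes a 15% event share, a TNBC HR of 0.65-0.70 and 6-16 degrees of freedom. At event shares of 25-30% the miss rate is about 60-80%. The exact percentage depends on these assumptions, but over this range a non-significant result says little. The wording on ruling out qualitative interaction is faulty for the same reason.

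The fault is confined to these two statements in an exploratory section. The planned estimates are sound and the primary analysis is unaffected.

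**What to change.** In section 12.2.1.4, and in the SAP where it repeats the rule:

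- Delete the sentence that concludes consistency, and state that a non-significant global test is not evidence of consistency.
- Base the consistency assessment on the subgroup HRs and 95% intervals already planned in section 12.2.1.3. From that same model, report the ratio of the hormone-receptor HRs with its 95% confidence interval, whatever the global result.
- Replace the phrase about ruling out qualitative interaction with: *tested for qualitative interaction; a non-significant result does not exclude it*.

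Do not write a fixed detectable ratio into the protocol, since it depends on the event split finally observed.

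The cost is a few lines of wording and one extra estimate from a model already planned. The primary test, alpha allocation and sample size do not change. The downside is that the sponsor can no longer declare consistency from a non-significant p-value alone.

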12.2.2 Analysis of secondary endpoints

OS and DDFS

OS and DDFS will be analysed at the time of the IDFS analysis as per the multiple testing procedure (MTP) outlined in [Section 12.2.5](#) and will use the same methodology and model as described above for the primary analysis of IDFS.

If applicable, a sensitivity analysis will be performed for DDFS and OS using the same model as described above for IDFS but based on all randomised patients confirmed to have *gBRCA* mutations by the central test. This analysis is only required if the analysis population differs from the primary ITT population. Subgroup analyses will also be conducted for DDFS and OS based on the same subgroups described above for IDFS.

DDFS and OS will be analysed at the time of the primary analysis for IDFS (when 330 IDFS events are reported).

The final OS analysis will be conducted once the trial follow up is complete (i.e. 10 years from when the last patient is randomised, estimated 14 years from first patient randomised assuming recruitment of 5 years).

In addition another analysis will be performed half way between the primary IDFS analysis and the final overall survival analysis (estimated around 10 years from first patient randomised but timings will be driven by the primary IDFS analysis once known). At this time point both DDFS and OS will be analysed and some alpha will be reserved for formal hypothesis testing. IDFS may also be updated if more information is available but this would be considered a supportive update of the primary analysis and no alpha will be reserved for IDFS.

For details on alpha spend and how this will be allocated across the planned analyses see [Section 12.2.6](#).

Incidence of contralateral invasive breast cancer, contralateral non-invasive breast cancer, new primary ovarian cancer, new primary fallopian tube cancer and new primary peritoneal cancer

The actual number and percentage of patients with new contralateral breast cancers (invasive and non-invasive), new primary ovarian cancer, new primary fallopian tube cancer and new primary peritoneal cancers will be presented. In addition a table summarising all reported new cancers (i.e. not just breast, ovarian, fallopian tube or peritoneal cancers) will also be produced.

As described in [Section 11.1.2.3](#), patients who have had a bilateral mastectomy prior to randomisation will be excluded from the analysis of new contralateral breast cancers (invasive and non-invasive) and patients who have had a bilateral oophorectomy prior to randomisation will be excluded from the analysis of new ovarian cancers and patients who have had their fallopian tubes removed prior to randomisation will be excluded from the analysis of new fallopian tube cancers.

The cumulative incidence of new primary contralateral invasive breast, new primary contralateral non-invasive breast, new primary ovarian cancers, new primary fallopian tube cancers and new primary peritoneal cancers will be compared between treatment groups using competing risk analysis (Gray test, [Fine and Gray 1999](#)). Death will be considered a competing risk for each endpoint. In addition, bilateral mastectomy after randomization will be a competing risk for the contralateral breast cancer analyses, bilateral oophorectomy will be a competing risk for the new primary ovarian cancers analysis and removal of the fallopian tubes will be a competing risk for the new primary fallopian tube cancer analysis. Hazard ratios and 95% confidence intervals from competing risks regression analyses ([Fine and Gray 1999](#)) adjusted for treatment and the stratification factors will also be presented – more details of these analyses are given in the SAP (Edition 2).

Safety

Safety data will be summarised descriptively in terms of AEs, vital signs, clinical chemistry & haematology and physical exam and will include data from the treatment and safety follow-up period. Cumulative incidence plots may also be presented for specific adverse events or groups events of interest. Further information on the summary of safety data will be provided in the SAP.

